VII.B.6 *Will any subjects receive a placebo in this study when, if they were not participating, they could be receiving an FDA-approved treatment for their condition?*
No

VII.B.11 *Is there a separate, written protocol that will be submitted in addition to this IRB New Project form? (Note: a grant application is not considered to be a protocol)*
No

VII.B.18 *Does this project involve the evaluation, or testing, of the safety and/or efficacy of a medical device?*
Yes

VII.B.19 *Describe in detail procedures in place for maintaining device shipment and receipt records:*
N/A

VII.B.20 *Who will be responsible for maintaining these shipment and receipt records?*
N/A

VII.B.21 *Describe in detail procedures in place for tracking use and disposition of devices described in this study:*
N/A

VII.B.22 *Who will be responsible for maintaining these use and disposition tracking records?*
The PI

VII.B.23 *Describe in detail procedures in place to limit access to authorized study personnel for the storage, control, and dispensing of the investigational devices. (For example, investigational devices are kept in a locked area away from approved devices or have a keyed interlock, and only study personnel authorized to dispense the device have the keys)*
The device will be in a locked cabinet in the laboratory of the PI.

VII.B.24 *Is the device FDA-approved for the way it will be used in this study?*
No

VII.B.25 *Is there an IDE (Investigational Device Exemption) for this device in this research project?*
No

VII.B.29 *Indicate the appropriate FDA status you and/or the sponsor are requesting for the use of this device in this study.*
Non-Significant Risk (NSR) device/software

VII.B.31 *Provide a detailed rationale for why this device meets the FDA definition of a Non-Significant Risk Device (NSR)*
Numerous studies used this device without any serious side effects. See attachments "tDCS Safety" and "tDCS Tolerability."

VII.B.32 *Provide a summary of prior investigations with this device.*
The PI used this device in previous studies without any serious adverse side effects.

[name], [name], and [name] (2020). Transcranial Direct Current Stimulation (tDCS) for the Treatment of a Multiple Sclerosis Symptom Cluster. *Brain Stimulation* 13(1), 263-264.

[name], [name], and [name] (2020). The Tolerability and Efficacy of 4 mA Transcranial Direct Current Stimulation on Leg Muscle Fatigability. *Brain Sciences* 10(1), 12. IF: 3.332

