- *Physician services or services provided by non-physicians who are credentialed to bill (ARNPs, Physician Assistants, etc.)*

- Yes

V.25.b *Will there be any procedures or services that may happen as part of a subject's regular medical care and as part of the study?*

No

V.25.c *Will any study equipment or devices be supplied by a study sponsor?*

No

V.25.e *Is there or will there be an internal budget for this study?*

Yes

V.25.f *Is there or will there be an external budget for this study?*

No

V.26 *The study involves Department of Nursing Services and Patient Care nursing, nursing resources or evaluates nursing practices at UI Health Care.*

No

VI. Subjects

VI.1 *How many adult subjects do you expect to consent or enroll for this project?*
150

VI.2 *What is the age of the youngest adult subject?*
18.0

VI.3 *What is the age of the oldest adult subject?*
80.0

VI.4 *What is the percentage of adult male subjects?*
50

VI.5 *What is the percentage of adult female subjects?*
50

VI.6 *How many minor subjects do you expect to consent or enroll for this project?*
0

VI.13 *Describe EACH of your subject populations*

- *Include description of any control group(s)*
- *Specify the Inclusion/Exclusion criteria for EACH group*

Fifty post-acute COVID-19 men and women with enduring fatigue will be recruited into one of two groups (tDCS or sham, n = 25 in each group), 50 post-acute COVID-19 men and women without enduring fatigue will be recruited into one of two groups (tDCS or sham, n = 25 in each group), and 50 subjects with no history of a COVID-19 diagnosis (controls) will be recruited into one of two groups (tDCS or sham, n = 25 in each group). For the COVID-19 subjects (fatigue and without fatigue), only those that are discharged from the UIHC COVID-19 inpatient clinic and/or that meet the CDC guidelines for discontinuing home isolation (i.e., fever-free for at least 24 hours, all symptoms improved after 10 days) will initially be

considered as long as they meet the rest of the following criteria:

Inclusion criteria (COVID-19 fatigue subjects):

- 18–80 yrs.
- Previous positive COVID-19 test
- >30 days since positive COVID-19 diagnosis
- Meet CDC guidelines (<https://www.cdc.gov/coronavirus/2019-ncov/hcp/duration-isolation.html>) for discontinuation of home isolation
- Meet the criteria for fatigue, based on the Chalder Fatigue Scale CFQ-11 case definition of fatigue

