Prospective participants will be recruited from the University of Iowa Hospitals and Clinics, Iowa City, IA, via advertisements throughout the university campus and community, mass email to the university staff, faculty and alumni (>35,000 recipients), and from the 'volunteer research' link on the clinical trials webpage on the University of Iowa Hospitals and Clinics website (<https://uihc.org/clinicaltrials/>). Other main recruiting tools will include advertisements in local newspapers (Iowa City Press Citizen, Cedar Rapids Gazette) and Noon News publications in the University of Iowa Hospitals & Clinics daily newsletter, which is available to the public and patients at various locations in the hospital. Drs. [name], [name], and [name] will also assess interest and provide referrals from visitors/patients in their clinics.

VI.16

Do you plan to recruit/enroll non-English speaking people?

No

VI.18

Do you propose to enroll any of the following in this study as subjects?

- *Employee of the PI or employee of a research team member*
- *Individual supervised by PI or supervised by member of research team*
- *Individual subordinate to the PI or subordinate to any member of the research team*
- *Student or trainee under the direction of the PI or under the direction of a member of the research team*

- No

VI.20

Will subjects provide any information about their relatives?

No

VI.23

Will anyone (other than the subject) provide you with information about the subject (e.g. proxy interviews)?

No

VI.26

Is this project about pregnant women?

No

VI.27

Will this project involve fetuses?

No

VI.28

Does this project involve adult subjects who may be incompetent or have limited decision-making capacity on initial enrollment into the study?

No

VI.32

Does this project involve subjects whose capacity to consent may change over the course of the study?

No

VI.37

Does this project involve prisoners as subjects?

No

VII.A. Project Description (A)

VII.A.1

Where will project procedures take place (check all that apply)?

- Other UI campus site - Department of Health and Human Physiology, Integrative Neurophysiology Laboratory; Pappajohn Biomedical Discovery Building (PBDB);
- UIHC - Department of Neurology; Department of Internal Medicine (COVID-19 Home Treatment Clinic); PET Imaging Center; Iowa Translational Vascular Physiology Lab ([name] PI) in C204 GH

VII.A.2

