During the first visit, the PI or research staff will provide potential subjects with the consent summary and full consent document. Subjects will be allowed to review the documents at their leisure and research personnel will answer all questions asked by the potential subject. The potential subject will be informed of all potential risks before signing the consent document. Subjects will in no way be coerced to sign the consent form and will be informed that it is their choice whether to volunteer for this study. Even after subjects sign the consent, they are free to withdraw from the study at any time for any reason. Consent may also be obtained via Zoom meeting or phone call prior to the Visit 1. After participant has been deemed eligible to participate in the study, research staff will conduct a zoom or phone call to walk through the study design and consent, as well as answer any questions the participant may have. Participants will then schedule their first five visits. After participants confirm their visit dates/times, they will be sent a confirmation email with detailed information about their visits, as well as a link to the consent form. Participant may then sign the consent document at the end of the Zoom or phone call and either scan email a copy or bring the signed consent with them to Visit 1.

During all study visits, all recommended precautions for mitigating the spread of COVID-19 during in-person research visits (e.g., face masks, face shields, extra cleaning before and after study visits, increased handwashing/sanitizing) will be followed as approved by our Departmental Executive Officer (DEO).

Mass emails to the University of Iowa and UHIC communities will be used to recruit participants who had a positive COVID-19 test 3 months or longer ago and who are either still having symptoms of post-COVID fatigue or are asymptomatic.

VII.D.37

Does the study include any form of deception (e.g., providing participants with false information, misleading information, or withholding information about certain study procedures)?

Examples:

- *Procedure includes a cover story that provides a plausible but inaccurate account of the purposes of the research.*
- *Participants will be provided with false information regarding the particular behaviors of interest in the research.*
- *Procedures include a confederate pretending to be another participant in the study.*

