- *Participants will be told that the research includes completion of a particular task, when in fact, that task will not be administered.*
- *Study is designed to introduce a new procedure (or task) that participants are not initially told about.*
- *If yes, a waiver of informed consent must be requested under question IV.3.*

• No

VII.E. Project Description (E)

VII.E.1

Will subjects be randomized?

Yes

VII.E.1.a

Will any subjects be blinded to which study arm they have been assigned?

Yes

VII.E.1.b

Does the protocol permit telling subjects their treatment assignment at the end of the entire study?

Yes

VII.E.1.c

Describe the circumstances under which subjects will be told what study arm they have been assigned.

At the end of all sessions, and upon request by the subject, the participant will be informed about the stimulation condition they experienced.

VII.E.2

Describe randomization scheme/assignment including ratio such as 1:1, 2:1 etc.

The study will be a double-blind, sham-controlled, randomized parallel design. Post-COVID-19 patients with fatigue, post-COVID-19 patients without fatigue, and subjects without a history of a COVID-19 diagnosis (controls) will be randomly assigned to one of two groups. One group will

receive tDCS (tDCS Group; n = 25 in each group of subjects; 75 total) and the other group will receive SHAM (SHAM Group; n = 25 in each group of subjects; 75 total). The study will involve nine sessions at the INPL.

VII.E.3

Will any questionnaires, surveys, or written assessments be used to obtain data directly from subjects in this study?

Yes

VII.E.4

List all questionnaires, surveys, written assessments and ATTACH each one to the application.

(NOTE: You are NOT prohibited from attaching copyrighted materials to this application)

Chalder Fatigue Scale

C19-YRS-Covid-Rehab-screening-tool

Fatigue Assessment Scale (FAS)

Fatigue Severity Scale (FSS)

EQ-5D-5L Quality of Life questionnaire

Visual analog scale for pain

COVID19 Severity Survey

Pittsburgh Sleep Quality Index (PSQI) (to determine sleep quality)

International Physical Activity Questionnaire (IPAQ) (to quantify recent physical activity levels)

VII.E.5

Does this project involve creating any audiotapes, videotapes, or photographs?

No

VII.E.6

Provide a detailed description in sequential order of the study procedures following the consent process - DO NOT cut and paste from the Consent Document.

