Describe study populations separately if they will be participating in different procedures - include CONTROL population if applicable.

DESCRIBE:

- **What subjects will be asked to do/what happens in the study (in sequential order)**
- **The time period over which procedures will occur**
- **The time commitment for the subject for individual visits/procedures**
- **Long-term followup and how it occurs**

Symptomatic subjects will be asked to complete 7 lab study sessions. The first lab session will take approximately 3.5 hours, the fifth lab session will take approximately 2 hours, and the tDCS sessions will take approximately 30 minutes. In all, full participation will take approximately seven weeks, with three week breaks between Lab Sessions 5, 6, and 7. Asymptomatic subjects will be asked to complete 1 lab study session, lasting approximately 2 hours.

Vascular study: In the initial session (Day 1) all subjects will 1) be consented, 2) undergo a blood draw to evaluate interleukin-6 values, lipids, glucose and c-reactive protein, complete 3) pulse wave velocity testing (arterial stiffness); 4) carotid compliance/stiffness with ultrasound 5) brachial artery flow-mediated dilation (vascular endothelial function) 6) the Fatigue Assessment Scale (FAS), 7) the Fatigue Severity Scale (FSS), 8) the visual analog scale (VAS) for pain, 9) cognitive testing 10) 1-100 symptom scale, 11) international physical activity questionnaire (IPAQ), 12) Pittsburgh sleep quality index (PSQI), and 13) the 6-minute walk test. For asymptomatic participants, this will mark the end of their study participation. For symptomatic participants, they will then have their first round of the intervention receiving either sham or tDCS.

The following four days will include receiving either 20 min of tDCS or sham treatment, depending on group randomization. Day 5 will include the same testing battery (blood draw, PET scan in 10 subjects from each group [i.e., those that got the pre scan], questionnaires, fatigue testing, walking test) as Day 1, except the subjects will not repeat the MRI scan, strength testing, or receive tDCS.

LONG-TERM EFFECTS OF tDCS: Three- and six-weeks following Day 5, participants will repeat the testing battery conducted on Days 1 and 5.

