The data that will be shared with the Medical University of South Carolina (MUSC) will be de-identified, age, race and ethnicity will be reported as required by NIH (see attached template that will be requested for reporting purposes) as part of a final report to MUSC.

X.7

Does your study meet the NIH criteria for a Certificate of Confidentiality or will you be applying for Certificate of Confidentiality?

No

XI. Data Analysis

XI.1

Describe the analysis methods you will use, including, if applicable, the variables you will analyze

The generalized estimating equation (GEE) framework will be utilized to assess changes over time in fatigue and quality of life measures. An interaction term between time and treatment will allow us to test the within- and between-treatment differences over all time points. Using histograms, variable distributions will be assessed to decide which link function to specify when modeling each outcome. To account for the inherent correlation that occurs in repeated measures data, we will cluster on subject ID. In addition to

examining the unadjusted relationship between the time-treatment interaction and each outcome, we will consider the addition of control variables, which will reduce the likelihood of unaccounted confounders. The control variables being considered for inclusion in the adjusted models are age, sex, and disease duration. For each outcome, models will be fit for all possible combinations of control variables. The predictor set that yields the smallest Akaike information criterion (AIC) will be considered the optimal control variable set to adjust associations between the main predictor and the outcomes. Statistical significance will be assessed at the $\alpha = 0.05$ level.

XI.2

Provide the rationale or power analysis to support the number of subjects proposed to complete this study.

The sample size calculation was based on the Fatigue Severity Scale data from our own preliminary data that assessed the effects of multiple sessions of 4 mA tDCS on fatigue in people with multiple sclerosis. The effect size of this difference = 0.91 (Cohen's d). With alpha fixed at 0.05, we would need 20 total subjects in each group (tDCS and SHAM; details below) to achieve 80% power in a two-tailed independent samples test. Therefore, to account for 20% data and subject attrition, we will recruit 25 subjects per group (150 total).

XII. Future Research

XII.1

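### Time since infection is open-ended from day 31, is worded differently in the recruitment text, and is neither a stratification factor nor a fixed term in the model

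*Combined protocol and SAP*

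**What the plan says.** - **Eligibility (VI.13).** Both COVID-19 groups, with and without fatigue, enter at ">30 days since positive COVID-19 diagnosis". No upper limit is given.
- **Recruitment (VI.15, VII.D.29).** VI.15 lists the routes: "Prospective participants will be recruited from the University of Iowa Hospitals and Clinics, Iowa City, IA, via advertisements throughout the university campus and community", together with a mass email, a website link, newspapers and clinic referrals. Only the mass-email text in VII.D.29 carries a longer window, seeking "participants who had a positive COVID-19 test 3 months or longer ago".
- **Randomisation (VII.E.2).** "The study will be a double-blind, sham-controlled, randomized parallel design". Subjects in each of the three populations "will be randomly assigned to one of two groups", with 25 planned per arm. Blocking and stratification are not mentioned.
- **Follow-up (VII.E.6).** For symptomatic subjects, "full participation will take approximately seven weeks", with assessments on Day 1, on Day 5, and three and six weeks after Day 5.
- **Analysis (XI.1).** A GEE model with a time-by-treatment interaction is to test both within- and between-treatment differences. "The control variables being considered for inclusion in the adjusted models are age, sex, and disease duration". The choice is made outcome by outcome: "The predictor set that yields the smallest Akaike information criterion (AIC) will be considered the optimal control variable set".
- **Hypotheses (I.5).** Hypotheses 1 and 2 are worded as improvement after the sessions and its presence at 3 and 6 weeks, that is, as change over time.

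**The concern.** Time since infection is a plausible predictor of how fatigue changes over the next several weeks. XI.1 itself names disease duration as a candidate control variable. Yet the eligibility rule lets it range from just over a month upwards, and the share of early patients will depend on how many come by email and how many by other routes.

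The randomised comparison at issue is the fatigue group, 25 v 25. (VII.E.6 ends asymptomatic participation after one session, which is a separate matter.) In arms of that size, a prognostic factor that is not stratified can be unbalanced by chance. If it is also left out of the model, its variation adds to the error term. The listed covariate is a weak safeguard. It is optional, it may be kept for one outcome and dropped for another, and it is not defined as time since positive test. Standard GEE also supplies no likelihood from which AIC could be computed.

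Within-arm improvement is more exposed, because natural recovery contributes to it directly.

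**Working it through.** **1. The plan's own figure (XI.2).** Inputs: d = 0.91, two-sided alpha 0.05, 80% power, 20% attrition. The two-sample t-test needs 19.96, so 20 per arm (power 0.801). Then 20 / 0.8 = 25 per arm, and 6 x 25 = 150. The stated sample size reproduces and does not depend on this point.

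**2. The two windows on the visit calendar.** Take Day 1 at day 31 after diagnosis, the earliest allowed:
- Day 5: 31 + 4 = day 35
- three-week visit: 35 + 21 = day 56
- six-week visit: 35 + 42 = day 77

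With 3 months taken as about 90 days, this patient finishes the trial before reaching the window in the email text. Conversely, everyone in the email window meets the VI.13 criterion.

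**3. Chance imbalance.** The documents do not give the share of early convalescents, so 30-50% is assumed. The number of early patients in each arm is taken as an independent binomial with n = 25. A gap of 5 patients is 20 percentage points.

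| Early share (assumed) | P(gap of 5 or more), 25 v 25 | P(gap of 4 or more), 20 v 20 |
|---|---|---|
| 0.3 | 0.164 | 0.226 |
| 0.4 | 0.193 | 0.258 |
| 0.5 | 0.203 | 0.268 |

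With exactly equal arms and a fixed number of early patients (hypergeometric), the 25 v 25 figures for the same shares are 0.217, 0.148 and 0.258. They are not monotone because only gaps of one parity can occur.

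**4. What a gap would do.** Assume early patients recover by an extra 0.3-0.8 SD; the documents give no rate. A 20-point gap shifts the difference by 0.20 x 0.3 = 0.06 SD to 0.20 x 0.8 = 0.16 SD, or about 7-18% of 0.91. The mean absolute gap is 2.6-2.8 patients, giving 2.6/25 x 0.3 = 0.03 SD to 2.8/25 x 0.8 = 0.09 SD. The standard error of the difference is sqrt(2/25) = 0.28 SD, or sqrt(2/20) = 0.32 SD with 20 completers.

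**5. Power if the factor is ignored.** With early share p and extra recovery r, and the planning SD of 1 taken to hold within the early and late groups, the total SD is sqrt(1 + r^2 p(1 - p)) and the effective d is 0.91 / SD.

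| r | p | SD | d | Power, 20 per arm | n per arm for 80% |
|---|---|---|---|---|---|
| 0.3 | 0.3 | 1.009 | 0.902 | 79.3% | 21 |
| 0.3 | 0.5 | 1.011 | 0.900 | 79.2% | 21 |
| 0.8 | 0.3 | 1.065 | 0.854 | 75.0% | 23 |
| 0.8 | 0.5 | 1.077 | 0.845 | 74.0% | 23 |

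**6. False positives.** In 40,000 simulated null trials of 20 v 20 with the factor ignored and an early share of 0.5, type I error was 0.051 (r = 0.5) and 0.049 (r = 1.0).

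**The case against.** The case against is substantial, and much of it stands.

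- **The windows are nested.** A sponsor may recruit more narrowly than the eligibility rule allows, and VI.13 does define who is eligible. What remains is a difference in wording that should be reconciled.
- **The design protects the main contrast.** A reader might infer that natural recovery is mixed unevenly into the tDCS-sham comparison and biases it. The documents do not support that. Randomisation balances time since infection in expectation, the concurrent sham arm carries the same recovery, and recruitment route cannot create a difference between arms. Chance imbalance is already part of the standard error.
- **The route split is not documented.** A reader might also infer that clinics supply early patients and email supplies late ones. Email targets late patients, but clinics and advertisements can yield anyone past day 30, and the advertisements are attachments not seen here.
- **No time course is given.** The 53.1% and 71% in the background are prevalences of fatigue from two different studies, not a decline over time. Faster recovery in early patients is plausible, but it is an assumption of this review.
- **The aims do not define persistent fatigue as 3 months**, and entry to the fatigue group already requires the CFQ-11 case definition.

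These points do not answer three things: the adjustment for disease duration is optional and undefined, stratification is not stated, and the within-treatment tests have no protection from natural recovery.

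**Conclusion.** The point holds as a modest weakness of design and analysis. The eligibility and recruitment texts should be reconciled, and a factor that the plan itself treats as potentially important should not be left to chance and an AIC search.

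The size is limited. Under the assumed early share, a gap of 20 points at 25 per arm occurs in about 16-20% of trials. Under the assumed extra recovery, leaving the factor out costs about 1 to 6 points of power. Both results rest on inputs that the documents do not give. The power figures also assume that the SD behind d = 0.91, which comes from multiple sclerosis data, does not already contain this variation. There is no systematic bias in the between-arm contrast and no inflation of type I error.

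The clearest exposure is interpretive: improvement within the tDCS arm, as Hypotheses 1 and 2 are worded, cannot be separated from recovery that would have happened anyway. The documents give no basis for saying which window is right. Severity is low to moderate.

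**What to change.** 1. **VI.13 and VII.D.29:** reconcile the wording on time since infection. Which window to use is for the investigators; this review does not choose it.
2. **VII.E.2:** stratify the fatigue-group randomisation by time since positive test, with two strata and a cut set before enrolment.
3. **XI.1:** define time since positive test and include it as a fixed, pre-specified covariate in place of AIC-selected disease duration. Because the worry is differing change over time, say whether it also interacts with visit.
4. **XI.1 and I.5:** base the efficacy conclusion on the between-arm contrast and report within-arm change as descriptive.

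The cost is a two-stratum list and one model degree of freedom (three more if the covariate interacts with the three post-baseline visits). The diagnosis date must be added to the variable list in VII.D.2.a, which omits it although VII.D.1.c already ticks diagnosis dates for access. The sample size need not change.
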